### Sample Size

Power was evaluated using a simulation study. In each simulation, a data set was constructed, combining actual prescribing data from mid-2019 through mid-2020 with simulated data from the subsequent year. The number of total pill days per clinician in the subsequent year was simulated to preserve the mean and standard deviation across clinicians from the prior year, with an assumed year-to-year correlation within clinicians of 0.90. We have previously observed that a small number of providers do a large amount of prescribing, and a large number of prescribers do very little prescribing. The small number of physicians who are likely to continue their high levels of prescribing, leading to high correlation. Clinicians were then randomized into intervention and control arms, with the intervention arm's number of pill days reduced by a constant amount. A linear regression of year 2's number of pill days was fitted with study arm and year 1's number of pill days as predictors. Heteroskedasticity-robust standard errors were used to compute p-values. Significance was defined as a p-value less than 0.05 evaluating the study arm effect in the model, and power was estimated as the percentage of simulations in which a significant difference was obtained. We performed 10,000 simulations to estimate power. Based on historical data, we estimate that about 65% of physicians included in our randomization list will see an eligible patient during the study period. We thus expect our analytic sample to include data from 96 physicians. With 48 physicians randomized to each arm, we will have 80% power to detect a mean reduction of 108 pill days, which is feasible. This simulation power analysis was performed using R v. 3.6.2 (<http://www.r-project.org/>).

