## Methods

### Inclusion Criteria

Eligible physicians for the EHR CDS tool intervention include physicians who provide ambulatory care in the UCLA health system and have generated a new antipsychotic prescription (e.g., Quetiapine, Olanzapine, Risperidone, Aripiprazole, Haloperidol, Clozapine) for eligible patients (described below) in the UCLA health system at least once between 1/1/2019-4/30/2021 (n = 149). Based on current prescribing patterns at UCLA, we estimate that the vast majority of physicians in the study (>75%) will only see this EHR CDS tool 1–2 times over a year, suggesting little impact on clinical workflow and lessening opportunities for contamination. Eligible physicians will be enrolled in the study during their first encounter with one of the patients during which a new antipsychotic medication order is initiated.

Inclusion criteria for patients will include: 1) having an assigned primary care physician (PCP) and/or assignment to an Accountable Care Organization (ACO) at UCLA Health, and 2) being part of the health system's EHR-based dementia registry. The health system's dementia registry uses a select group of ICD-10 codes included in the patient's problem list to identify patients with ADRD, without age restrictions (Table 1). This ICD-based approach was implemented by the health system as an update to a previously published approach. To measure the specificity of this method for correctly classifying patients as having ADRD, physicians on the study team (board-certified geriatrician, palliative care specialist, and

primary care general internist) conducted an implicit review (e.g., expert clinician diagnostic judgment) on a random sample of 30 registry patients; 29 out of 30 (97%) had ADRD.

*Table 1: Dementia international classification of diseases 9th and 10th revision (ICD-9 and ICD-10) codes.*

	ICD-9 codes	ICD-10 codes

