visit summary; and 3) for physicians who do not cancel their prescription order, an automatic default to a low dosing and low number of pill days prescribed in the order set (30 pill-days). The study team consulted a pharmacist expert (GC) on appropriate defaults for antipsychotics in terms of dosing, frequency, and number of pills supplied. For example, currently in the UCLA EHR quetiapine defaults to 25 mg by mouth once daily 90 tabs x 3 refills, totaling 360 pill-days. The study team will change the default to 25 mg by mouth once daily 30 tabs with no refills, totaling 30 pill-days. Physicians will be free to increase amounts as they desire and thus this EHR CDS will not include a “hard stop.” The study team opted against the hard stop in acknowledgement of the clinical complexity of this vulnerable patient population and in recognition of the fact that an outright ban on such prescriptions may have unintended consequences including but not limited to endangerment of caretakers or cohabitants. The EHR CDS tool will fire when the eligible physician places a new antipsychotic order for an eligible patient. Once the CDS tool fires and the physician places the order for either the original dose or a lower dose, the patient becomes no longer eligible due to having an active antipsychotic order. Therefore, it will not fire for prescription renewals.

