## Statistical Analysis Plan

### Randomization & Blinding

A statistician not involved in data collection will randomize each eligible clinician to the intervention or control group; physicians will remain in the same arm of the study throughout the entire study period. The randomization of clinicians will be stratified by the number of new antipsychotic prescriptions during the baseline year: 1 vs. 2–3 vs. 4 or more new prescriptions. The randomization of the clinicians was incorporated into the EHR, tagging the providers as either EHR Intervention or EHR Control in a list created for this intervention. The study team will randomize physicians rather than patients to minimize

contamination. Contamination occurs when a physician sees a patient in the intervention arm at one time point, learns from the intervention that ordering antipsychotic medications is wrong and/or difficult, and then avoids prescribing these medications in the future, even when seeing a patient in the control arm. Because physicians will on average receive the intervention 1–2 times during the study period, inter-physician contamination will be minimal. Moreover, the CDS tool will only trigger for a new antipsychotic order, defined as an antipsychotic prescription for a patient who has not had an active antipsychotic prescription within the previous 12 months. This intervention will be implemented as part of a quality improvement effort; clinicians will not be blinded to receiving the intervention.

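### The stated 80% power rests on an assumed year-to-year correlation of 0.90 that has only qualitative support and no sensitivity range, and the power falls quickly if the true value is lower.

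*Combined protocol and SAP*

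**What the plan says.** The Sample Size section describes a simulation of 10,000 runs. Year 1 is real prescribing data from mid-2019 to mid-2020. Year 2 is generated to keep year 1's mean and SD, "with an assumed year-to-year correlation within clinicians of 0.90". The intervention arm is lowered by a constant, and year-2 pill-days are regressed on arm and year-1 pill-days with robust standard errors. The result is "With 48 physicians randomized to each arm, we will have 80% power to detect a mean reduction of 108 pill days, which is feasible".

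The reason offered for the correlation is that "a small number of providers do a large amount of prescribing, and a large number of prescribers do very little prescribing", and that the heavy prescribers will probably remain so. No SD, mean, estimated correlation or alternative value is reported.

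Four other places bear on the value:

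- Randomization & Blinding: "Because physicians will on average receive the intervention 1–2 times during the study period", contamination is expected to be minimal. The strata are 1, 2–3, and 4 or more new prescriptions in the baseline year.
- Intervention: the current quetiapine default is given, as an example, as "90 tabs x 3 refills, totaling 360 pill-days".
- Inclusion Criteria: the 149 physicians were identified by at least one new order from 1 January 2019 to 30 April 2021. More than 75% are expected to see the tool only 1–2 times a year.
- Statistical Analyses: the planned primary model adjusts for the baseline number of new prescriptions, gender and specialty. It does not adjust for baseline pill-days.

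**The concern.** When a baseline value is used as covariate, the residual variance is proportional to 1 − r². Near r = 0.90 this changes fast: 1 − r² is 0.19 at 0.90 and 0.36 at 0.80, so the residual variance almost doubles. A qualitative argument that the correlation is high cannot separate 0.90 from 0.80.

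The stake is how a non-significant result would be read. If the correlation is well below 0.90, the trial could miss a true reduction of 108 pill-days about as often as it finds it, while the plan presents it as having 80% power. Type I error and bias are not affected.

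**Working it through.** **Inputs.** From Sample Size: 48 per arm, 108 pill-days, 80% power, r = 0.90, significance at 0.05. Assumed: a two-sided test, since sidedness is not stated. Not given: the SD of pill-days.

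**Step 1: the plan's own figure.** Without the SD the 80% cannot be reproduced independently. It can only be used to calibrate:

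- Residual SD = 108 / [(1.960 + 0.842) × √(2/48)] = 108 / (2.802 × 0.2041) = 188.9.
- Total SD = 188.9 / √(1 − 0.90²) = 188.9 / 0.436 = 433.

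The sample size agrees with the text: 149 × 0.65 = 96.85, stated as 96.

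**Step 2: vary r, holding SD 433 and 48 per arm.** Residual SD = 433 × √(1 − r²). Power for 108 is from the noncentral t with 93 df. The detectable difference is 2.802 × 0.2041 × residual SD (normal approximation).

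| r | Residual SD | Power for 108 | Detectable at 80% |
|---|---|---|---|
| 0.90 | 189 | 79% | 108 |
| 0.85 | 228 | 63% | 131 |
| 0.80 | 260 | 52% | 149 |
| 0.50 | 375 | 29% | 215 |

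The 79% rather than 80% in the first row is the t correction. A simulation in the plan's form (assumed skewed baseline scaled to SD 433, robust standard errors, 4,000 runs) gave 78.3% at 0.90, 51.9% at 0.80 and 27.8% at 0.50, so the table does not depend on normality.

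**Step 3: what 0.90 requires of order counts and sizes.** Suppose each physician has a stable rate, yearly counts are Poisson, and the mean rate is m. Then r = 1 − m × (mean-square order size) / SD². Setting r = 0.90 gives a root-mean-square order size of at most √(0.10 × 433² / m):

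- m = 1: 137 pill-days
- m = 1.5: 112 pill-days
- m = 2: 97 pill-days

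With 1.5–2 orders a year, 90-day orders allow r up to 0.91–0.94, and 180-day orders only 0.65–0.74.

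**Step 4: what 0.90 requires of concentration.** For order counts alone with a constant order size, r = V / (V + m), where V is the variance of rates between physicians. Let the remaining physicians average 1.5 orders a year:

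- 20% at 6 orders: V = 3.24, m = 2.40, r = 0.57.
- 20% at 10 orders: V = 11.56, m = 3.20, r = 0.78.
- 10% at 20 orders: V = 30.80, m = 3.35, r = 0.90.
- 5% at 24 orders: V = 24.05, m = 2.63, r = 0.90.
- One physician of 96 at 44 orders: V = 18.62, m = 1.94, r = 0.91.

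Only the last keeps the overall mean within 1–2.

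**Step 5: the covariate.** The simulated 0.90 links year-2 pill-days to year-1 pill-days. The planned model uses a baseline count of prescriptions, so even a true 0.90 for pill-days need not carry over to the planned analysis.

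**The case against.** The best reply is that the plan does give a reason, and a sensible one: persistent heavy prescribers in a skewed distribution produce a high correlation. The stratum of 4 or more orders has no upper limit, the upper quarter of physicians is left undescribed, and Step 4 shows that about 0.90 is attainable. Real orders may also be short. This stands, and it rules out several stronger readings.

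- A reader might infer that the plan's order counts and sizes show the correlation to be below 0.90. They do not. No observed order size is given, the SD is back-solved using 0.90 itself, and Poisson counts are an assumption. Counts less variable than Poisson would loosen the cap, while drifting rates would tighten it.
- A reader might put the 360-day default into the formula and conclude that the correlation is near zero. At 1.5 orders a year the order noise alone would be √1.5 × 360 = 441, above the total SD of 433. That shows inputs that do not belong together. The 360 figure is one drug's default, offered as an example, and typical orders may be much shorter.
- A reader might infer that the sponsor held two years of pill-day data and ignored them. The 28-month window was used to identify physicians. The documents do not say that pill-days were extracted for all of it, or were available when the simulation was run.

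It is also fair that the SD, the constant-shift effect and the 65% participation rate matter to the power, and that the trial's final standard error will show the precision achieved. Neither supplies the missing support for 0.90.

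**Conclusion.** The concern holds as one of an unsupported and influential input. The claim of "80% power to detect a mean reduction of 108 pill days, which is feasible" depends on a correlation for which the plan offers a direction but no value. A shortfall of 0.05 costs about 16 points of power (79% to 63%), and one of 0.10 about 27 points (79% to 52%).

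The value is strained, not refuted. At an average of 1–2 orders a year it needs both short orders (root-mean-square about 97–137 pill-days or less) and heavy concentration in very few physicians. It does not follow that the trial is underpowered: if the measured relation is near 0.90 in the covariate actually used, the stated power stands.

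The power figures rest on the back-solved SD of 433 and a two-sided 0.05 test. The order-size limits rest also on Poisson counts with stable rates.

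**What to change.** 1. Take EHR order data for two non-overlapping 12-month periods, for example within January 2019 to April 2021.
2. Estimate the physician-level relation between year-2 pill-days and the covariate in the planned model, the baseline number of new prescriptions. Alternatively, change the planned model to adjust for baseline pill-days, so that it matches the simulation, and estimate that correlation.
3. Do this among physicians with an eligible patient in the second period, the group that the 96 represents. State that selection on at least one order in the window can distort the estimate: a physician with none in one year is more likely to have some in the other.
4. Rerun the simulation at the estimate and at both ends of its confidence interval. Report the mean and SD of pill-days, and restate the power for 108 pill-days or the detectable difference at 96 physicians.

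The cost is one data pull and one rerun of existing R code. The stated power may come out less favourable. No extra enrolment is proposed.
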